5.1. Overall Design

It is hypothesized that daily wear of the study device will result in significant improvements in patient-reported symptom severity. It is also hypothesized that the effects from active study device treatment will be significantly greater than effects from sham treatment. In both cases, it is hypothesized that improvements will be sustained post-treatment.

This study is designed as a randomized, double-blind, sham-controlled, two-arm trial consisting of an eight-week treatment period (active study device or sham), followed by one required follow-up four weeks later (at week 12). After the required follow-up evaluation, the active device group can optionally continue to report symptom changes for an additional 8 weeks. The sham group participants can elect to wear the active study device for 8 weeks after completing their week 12 follow-up evaluation of the sham device. For both groups, completion through the optional follow-ups results in a 5-month patient duration.

There are two study groups: the active device group receiving the active study device and the sham group receiving a non-active sham device. Subjects will be informed that they have a 50:50 chance of receiving treatment or a sham. They will also be informed that if they receive sham device, they will be offered the active device 4 weeks into the post-treatment period. However, all subjects will not know what treatment they are on until the conclusion of the trial. Study devices are shipped directly to enrolled subjects from the Sponsor's designated shipping associate, which blinds site staff to group assignment.

There are (at minimum) three physical research sites but subjects are primarily enrolled remotely. The physical research sites are clinics that local subjects can physically go to if needed (e.g., medical concern, AE). Enrolled subjects are assigned to the PI of the geographically closest physical site.

Subjects are enrolled following confirmation of CTS in one or both wrists via a recent Nerve Conduction Study (NCS) and are asked to wear the assigned device daily for 8 weeks. The NCS is an electrodiagnostic technique used to confirm clinical diagnosis of CTS, with a 56% to 85% sensitivity and at least 95% specificity for CTS.¹⁵ The primary outcome measure, Symptom Severity Score (SSS) of the Boston Carpal Tunnel Questionnaire (BCTQ), is evaluated at:

- Baseline
- Once every 2 weeks during the 8-week treatment period
- 4 weeks after the end of treatment (at week 12)

After week 12, the active device group can continue to complete follow-ups every 4 weeks for another 8 weeks. At the end of week 12, the sham group will be given the opportunity to wear the active study device for 8 weeks. These subjects will be evaluated once every 2 weeks during an 8-week treatment period with the active study device (similar to the initial treatment period).

For visual representation of the study design, see Section [2.2 Schedule of Events \(SOE\)](#).

5.2. Scientific Rationale

The study device was used in a pilot clinical trial (PPS-CTMD-15-001, ClinicalTrials.gov ID NCT02534493) that finished in October 2016 with promising results. Participants showed an average improvement in symptom severity scale (SSS) score of the Boston Carpal Tunnel Questionnaire (BCTQ) of 0.59 ± 0.68 points at 4 weeks (end of treatment period) compared to baseline SSS scores. After the 4-week treatment period, symptoms continued to improve for a total of 0.79 ± 0.74 points lower SSS compared to Baseline at 12 weeks.⁹ These results motivate the primary objective of this study.

The pilot study investigated the effects of the study device up to 4 weeks, but the trajectory of SSS did not indicate that improvement plateaued by 4 weeks. Thus, the treatment period is extended to 8 weeks in this study to determine if improvements continue with longer-term wear.

Analysis of the unilateral vs bilateral CTS patients showed a stark contrast in response. SSS of the unilateral patients improved 0.9 ± 0.5 points at 4 weeks and up to 1.2 ± 0.5 points at 12 weeks. In contrast, the bilateral patients appeared to show no improvement; however, the pilot study was not powered to detect differences in unilateral and bilateral subgroups. This difference is being explored as an exploratory objective in this study.

Most participants described the study device as being very comfortable and easy to wear. However, there were occasional comments about discomfort from the edges of the device. In Aim 1 of the NIBIB grant R44 EB024713-01, a series of experiments were conducted to investigate the applied pressures on wrists using tactile pressure sensors, the changes in median nerve dimensions using magnetic resonance imaging (MRI), and the changes in carpal tunnel or median nerve compression pressures in cadavers when the study device was applied to the wrist. This allowed the study device to be re-designed to fit a wider range of people and to reduce uncomfortable pressure points. A user feedback survey is incorporated in the present study to improve user satisfaction, which is critical for any practical application and success.

6. STUDY POPULATION

The study population includes adults ages 21 to 65 of all races and ethnicities and of both genders who meet the inclusion/exclusion criteria below. We expect to recruit at least twice as many women as men because studies have found that approximately 3 times as many women are affected by CTS as men.^{10,11}

6.1. Inclusion Criteria

1. Ages 21-65
2. Clinically diagnosed with mild to severe carpal tunnel syndrome (CTS)
3. CTS diagnosis confirmed by a nerve conduction study (NCS) performed within the past 24 months OR at enrollment/baseline visit
 - a. CTS severity determined via AANEM criteria¹³
 - b. Bilateral CTS accepted (worse wrist via NCS and/or BCTQ is designated as the study wrist)

4. BCTQ SSS ≥ 2
5. Reliable access to and ability to use Internet, Wi-Fi, or mobile data through computers, mobile devices, laptops, and/or tablets
6. Willing to abstain from any other treatment or therapies for CTS throughout the study
7. Ability to read and write English, or has a reliable person to assist with reading and writing English

6.2. Exclusion Criteria

1. Other upper extremity neuropathies (e.g., epicondylitis, radial nerve neuropathies, ulnar nerve neuropathies)
2. Double crush syndrome
3. Cervical stenosis
4. Brachial plexopathy
5. Wrist fractures or cysts
6. Prior wrist surgeries, especially carpal tunnel release surgery
7. Injection of corticosteroid/cortisone into the wrist or hand within the past 6 months
8. Thyroid disease
9. Rheumatoid arthritis
10. Diabetes
11. Systemic diseases
12. Connective tissue diseases
13. Fibromyalgia or chronic pain syndrome
14. Diabetic neuropathy
15. BMI ≥ 40
16. Participation in other research studies or clinical trials currently or within the past 2 weeks.

6.3. Prior/Concomitant Medications or Therapies

1. No other therapies for carpal tunnel syndrome may be undertaken during the study (e.g., hand therapy, wearing wrist brace/splint, corticosteroid/cortisone injection to the wrist, carpal tunnel release surgery).
2. Hand stretching exercises and stretches indicated for carpal tunnel syndrome are allowed.
3. Yoga, tai chi, and other fitness programs often associated with helping with carpal tunnel syndrome are allowed but should be reported.
4. No narcotics, opioids, or other prescription painkiller or pain medication may be taken during the study and must not have been taken for 3 months prior to enrollment.
5. Over-the-counter low-dose NSAIDs or painkillers (e.g., Advil, Tylenol) are allowed if taken only as needed (e.g., to relieve pain caused by injuries, migraines, period cramps, menstrual pain) and taken no more than the recommended doses on the medication's label (e.g., no more than 6 tablets in 24 hours).
6. Pain creams should not be applied to the wrist where the device is applied.

6.4. Enrollment Determination

Subjects that pass the inclusion/exclusion criteria, have provided or completed a NCS report confirming mild to severe CTS diagnosis, and have signed the Informed Consent Form (ICF) are considered enrolled in the study.

6.5. Screen Failures

Screen failures are defined as subjects who consent to participate in the clinical trial (i.e., sign the ICF) but are not subsequently randomized to a study intervention or enrolled. Some reasons for not enrolling after signing the ICF include the subject deciding not to participate or the discovery of disqualifying criteria after signing the ICF.

In certain cases, a subject may need an NCS performed under their primary care provider after having signed the ICF. If the NCS report does not meet the inclusion criteria, the subject is not enrolled and is categorized as screen failure.

6.6. Strategies for Recruitment & Retention

Each site will advertise and recruit subjects per each site's best practices and following applicable GCP, HIPAA, and all local to federal laws. Recruitment may be supplemented with IRB-approved physical advertisements such as flyers or cards and with IRB-approved digital advertisements on webpages and social media. Sponsor may supply advertising and marketing materials at Sponsor's discretion or as needed by the sites.

Sites may identify eligible subjects from their patient or volunteer databases or from their (electronic) medical records. Physicians at each site may identify eligible subjects during routine appointments, at which point the physician should offer information about the study to the patient. Sites may also obtain referrals from nearby or partner clinics.

Before enrollment, all subjects are informed that there is a 50/50 chance of receiving the real device or the sham device. However, the sham group will be given the opportunity to undergo treatment with the real device upon completion of the main part of the trial (after Week 12). This method seeks to increase fairness of participation and improve retention of sham group participants.

7. STUDY PROCEDURES

7.1. Screening, Informed Consent and HIPAA

Subjects that pass the pre-screening questionnaire and meet all inclusion/exclusion criteria will be asked to participate in the study. The study design, objective, procedures, schedule, and participation parameters/criteria will be provided to and/or discussed with subjects prior to enrollment. Subjects wishing to participate must read and complete the Informed Consent Form (ICF) and sign an "Authorization for Use and Disclosure of Health Information for Research" release as a component of the ICF (HIPAA authorization) prior to undergoing any study-related procedures.

The ICF/HIPAA Authorization may be sent electronically to the subject. Subjects and designated site staff may sign electronically or can physically sign but must provide a scanned signed copy ICF/HIPAA Authorization to the site for documentation.

Documentation of screening, eligibility confirmation, and reasons for ineligibility or non-participation will be kept in a Screening Log.

7.2. Enrollment, Baseline Assessment, and Randomization

7.2.1. Enrollment Procedures

After the subject has passed the pre-screening questionnaire, the subject will begin enrollment, which includes reading and signing the ICF/HIPAA Authorization, completing the Enrollment Form which includes the BCTQ and NPRS, and confirmation of CTS diagnosis via NCS. After confirming meeting all inclusion/exclusion criteria, the subject is considered enrolled. The subject will be randomized into either the active device group or the sham group and assigned a Subject ID.

Once the subject is enrolled, study devices are shipped (expedited) to the subject to begin treatment as soon after enrollment as possible. If a subject is bilateral, only the worse wrist (via NCS severity and/or SSS score) will be treated during the study. If NCS severity and/or SSS score are the same for both wrists, the dominant wrist will be treated. Standardized training and instructional materials will be provided to the subject on how to use the study devices, how and when to complete surveys, Diaries, etc.; how and when to report AE's/SAE's; and how to contact site staff or PI.

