7.2.3. Baseline Assessment

The Enrollment CRF captures Baseline assessment measures. These include:

- Date of birth/age
- Gender
- CTS severity (mild, moderate, or severe, from NCS)
- CTS diagnosis by hand (unilateral/bilateral, right/left/both)
- BCTQ and NPRS for affected hand(s)

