7.3. Treatment Period

The Treatment Period begins the first day that the subject begins wearing the device. Electronic Diaries are sent to subjects every day from the first day of treatment for 56 days. Subjects should be reminded if (s)he does not complete an entry. If 3 or more consecutive diary entries are missed, the site should contact the subject to remind them to complete entries or they could be withdrawn from the study. No more than 3 consecutive Diary entries and no more than 25% of total entries should be missed (14 out of 56 diary entries), but withdrawal due to missed Diary entries will be up to Sponsor after evaluating the situation

Follow-up surveys are electronically sent to subjects every 2 weeks from the subject's first day of device wear up to 8 weeks. The subject should complete the surveys within 3 days and reminders should be sent if the subject does not complete the survey. If the subject does not complete the survey within 3 days, the site should follow up with the subject to remind them to complete the survey and address any issues preventing the subject from completing the survey. All subject correspondences and contact attempts should be documented.

On the last day of treatment, the subject will complete a User Feedback Survey. This should be completed within 5 days.

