10.2. Sample Size Determination

A total of 102 subjects are required for this study, with 51 in each group.

The outcome measure used for calculations in the SSS of the BCTQ, which ranges from 1 to 5 with 1 being no symptoms (improved) and 5 being the worst symptoms (worsened).

A moderate effect size of 0.4 was chosen, assuming that study device efficacy is 0.4 greater than sham.

The pilot study experienced a drop-out rate of 20% (2 out of 13 total). With the longer treatment and follow-up times of this study, a higher drop-out is expected. Therefore the sample size calculation is modified by an estimated attrition rate of 25%.

The primary objective examines the 8 week vs baseline within-active group SSS change. Sample size determination explanation. The power analysis using the above results in a significance level of 0.05 and a power of 0.94*.

The secondary objective examines the change in SSS after 8 weeks between the active study device and sham groups. Sample size calculation is based on a parallel, one-sided t-test power analysis to identify an effect size of 0.4, standard deviation of 0.7 (based on the pilot study PPS-CTMD-15-001), significance level of 0.05, power of 0.8, and an estimated attrition rate of 25%.

The sample size was chosen to meet both the primary and secondary objectives.

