10.5. Statistical Analyses

The primary efficacy endpoint is the improvement (reduction) in SSS of the treatment group at 8 weeks after the first day of device wear. The primary efficacy endpoint will be analyzed using a paired, one-sided t-test.

The secondary efficacy endpoint is the improvement (reduction) in SSS of the treatment group compared to the sham group at T4 (8 weeks after the first day of device wear). The secondary endpoint will be analyzed using a two sample one-sided t-test.

A repeated measures analysis of variance will be used to evaluate changes over time in both the active and sham groups.

The exploratory endpoints will be analyzed using descriptive methods.

Safety analyses will be performed on all subjects that received treatment.

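### Baseline SSS is taken at enrollment, before the device ships, but Week 8 is counted from first wear, so the uncontrolled primary change includes an untreated interval with no stated maximum

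*Combined protocol and SAP*

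**What the plan says.** **Where baseline comes from.** Section 7.2.1 describes enrollment as signing the consent form, then "completing the Enrollment Form which includes the BCTQ and NPRS, and confirmation of CTS diagnosis via NCS". Section 7.2.3 confirms the source: "The Enrollment CRF captures Baseline assessment measures". Section 6.1 requires an SSS of at least 2 for entry, and sections 7.2.1 and 8.1 ship the device only after enrollment. The baseline score must therefore exist before shipment.

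**Where Week 8 comes from.** Section 7.3 states: "The Treatment Period begins the first day that the subject begins wearing the device". It adds: "Follow-up surveys are electronically sent to subjects every 2 weeks from the subject's first day of device wear up to 8 weeks". Section 10.5 defines the primary endpoint as the "improvement (reduction) in SSS of the treatment group at 8 weeks after the first day of device wear".

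**How the two are joined.** Section 10.2: "The primary objective examines the 8 week vs baseline within-active group SSS change". Section 10.5: "The primary efficacy endpoint will be analyzed using a paired, one-sided t-test".

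**What the Schedule of Events shows.** Section 2.2 puts enrollment, nerve conduction study (NCS) and BCTQ together at Week 0, Day 0, with the next BCTQ at Week 2 and Week 8 at Day 56. No separate BCTQ is scheduled at first wear.

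**What bears on the gap.** Section 7.2.1 calls for expedited shipment and a prompt start, and section 8.1 for re-sending a package that has not arrived by its expected date. Section 6.5 says that in certain cases "a subject may need an NCS performed under their primary care provider after having signed the ICF". No section gives a maximum number of days from the Enrollment Form to first wear.

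**The concern.** A baseline-to-Week 8 change is meant to describe eight weeks of wear. As written, it describes eight weeks of wear plus whatever time passed between the Enrollment Form and the first day of wear. That extra time differs between subjects and is not bounded.

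This matters because the primary test has no control arm. A change in symptoms before the device is worn enters the paired difference in the same way as a change during wear, and would be credited to the device. The exploratory question of whether improvement appears before Week 8 is affected likewise, since the Week 2, 4 and 6 surveys are also counted from first wear but compared with the enrollment score.

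Separately, the Schedule of Events and section 7.3 disagree on what Day 0 is. For a device shipped after enrollment, the enrollment day and the first day of wear cannot in general be the same day.

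**Working it through.** **1. The plan's own figures (section 10.2).** Inputs: difference 0.4, SD 0.7, one-sided alpha 0.05, power 0.80, attrition 25%.

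- Per arm: n = 2 × (1.645 + 0.842)² × 0.7² / 0.4² = 37.9, so 38. Then 38 / 0.75 = 50.7, so 51 per arm and 102 in total. This matches.
- Primary power, 38 completers, paired: 0.4 × √38 / 0.7 = 3.52. With a two-sided alpha of 0.05, Φ(3.52 − 1.96) = 0.94, which matches. The one-sided test named in section 10.5 gives Φ(3.52 − 1.645) = 0.97.

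Neither figure is in dispute here, and the sample size does not depend on this point.

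**2. Elapsed time in the primary change.** The documents give no gap length, so these gaps are assumed. Interval = 56 + gap; untreated share = gap / (56 + gap).

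| Assumed gap (days) | Baseline to Week 8 (days) | Untreated share |
|---|---|---|
| 3 | 59 | 5% |
| 7 | 63 | 11% |
| 14 | 70 | 20% |
| 28 | 84 | 33% |

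**3. A rate for illustration only.** The pilot (section 5.2) reports SSS 0.59 below baseline at 4 weeks, when wear stopped, and 0.79 below at 12 weeks: (0.79 − 0.59) / 8 = 0.025 points per week off device. Applying this before wear is an assumption. It gives 0.025 points for a 1-week gap and 0.10 for a 4-week gap; the latter is 0.10 / 0.4 = 25% of the target.

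An arm average depends on the mix. If, for illustration, 80% waited 1 week and 20% waited 4 weeks: 0.8 × 0.025 + 0.2 × 0.10 = 0.04 points, a tenth of 0.4.

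**4. Effect on the primary test when wear has no effect.** With 38 completers and SD 0.7, the standard error is 0.7 / √38 = 0.114. The one-sided critical value is t(37) = 1.687, so the smallest significant mean fall is 1.687 × 0.114 = 0.19 points. The rejection probability is the upper tail of a noncentral t with 37 degrees of freedom and noncentrality (fall / 0.7) × √38.

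| Assumed mean pre-wear fall | Noncentrality | Rejection probability |
|---|---|---|
| 0 | 0 | 5% |
| 0.025 | 0.22 | 8% |
| 0.05 | 0.44 | 11% |
| 0.10 | 0.88 | 22% |

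If symptoms worsened before wear, the noncentrality would be negative and the rejection probability would drop below 5%.

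**5. The randomised comparison.** Device type does not alter the enrollment or shipping steps, so the pre-wear interval is expected to be the same in both arms. It adds no expected bias to active versus sham. It may add some noise to the change scores; the documents give nothing from which to size it.

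**The case against.** The strongest reply is that the gap is short and its effect unknown.

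- **Length.** A reader might infer an unlimited wait. The documents do not support that: shipment is expedited, a prompt start is required and undelivered packages are re-sent. What is missing is a stated maximum.
- **NCS order.** A reader might infer that every subject fills in the BCTQ and then waits for an NCS. Section 7.2.1 lists the enrollment steps without fixing their order, section 6.1 accepts an NCS from the past 24 months or at the enrollment/baseline visit, and section 7.2.3 records NCS severity on the same form as the BCTQ. A later NCS is the exception in section 6.5, which does not say that the BCTQ comes first.
- **Drift.** The 0.025 per week is change after four weeks of wear in a 13-subject pilot. It may be carry-over and is not an untreated rate. No untreated data are given, so even the sign is open. An arm average of 0.10 would need every subject to wait about four weeks.
- **Recall.** Appendix I asks about the past two weeks. For a gap of a few days, enrollment and first-wear forms would cover largely the same period.
- **Larger problem.** At the same illustrative rate, the eight weeks of wear would carry 8 × 0.025 = 0.20 points of drift, far more than a 1-week gap.
- **Remedy.** A first-wear score is taken after randomisation, with the device in hand. The sham has a cushion (section 3.2), so a guess at allocation could colour the answer, and remote completion before application cannot be verified.

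All of this stands as a limit on size. It does not remove the mismatch between the baseline and the Week 8 clock, or the conflicting Day 0. The last objection is met by restricting the first-wear score to the within-arm change and the exploratory time course, and leaving the pre-randomisation score as baseline for active versus sham.

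**Conclusion.** The point holds as a cheap improvement. The text establishes that baseline SSS precedes randomisation and shipment, that Week 8 runs from first wear, that no maximum interval and no first-wear BCTQ are specified, and that section 2.2 and section 7.3 need to be reconciled on Day 0. The single-arm paired test cannot separate change before wear from change during it.

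The gap is probably days for most subjects, and longer only for the few who complete the form and then await an NCS or a re-sent package. For a gap of days the effect is likely to be small. The range of about 8% to 22% rests on assumed mean falls of 0.025 to 0.10 points, 38 completers and SD 0.7; the upper end would need long waits throughout the arm. It should not be read as an estimate of bias, and nothing here suggests bias in the randomised comparison or a need to change N.

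The fix would also lessen regression to the mean from selecting on SSS of at least 2, because the analysis baseline would no longer be the screening score. Placebo response and natural course would stay in the primary test even with a gap of zero.

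**What to change.** 1. Reconcile Day 0 between the Schedule of Events (2.2) and section 7.3, with enrollment and first wear shown as separate events.
2. Send the online BCTQ on the first day of wear, to be completed before the device is applied, with the first Diary. In sections 4 and 10.5, define that score as baseline for the within-arm primary change and the exploratory time course.
3. Keep the Enrollment Form SSS for eligibility, as baseline for the active-versus-sham comparison, and as the fallback when the first-wear form is missing.
4. Report the enrollment-to-first-wear interval by arm. Section 11.1 already dates each form and Diaries start on the first day of treatment, so it should be derivable.
5. Add a sensitivity analysis of the primary change using the enrollment baseline for everyone.

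**Cost.** One more short online form on a day when a Diary is already sent, and protocol wording. Some first-wear forms will be missing, so the fallback will mix two kinds of baseline; item 5 shows whether that matters. The first-wear score is self-reported by a subject who already holds the device. The sample size stays at 102.
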